2 LIST OF ABBREVIATIONS AND DEFINITIONS OF TERMS

Abbreviation	Term
AE	adverse event
ANCOVA	analysis of covariance
ANOVA	analysis of variance
BOCF	baseline observation carried forward
BMI	body mass index
CDC	Centers for Disease Control and Prevention
CI	confidence interval
CMH	Cochran-Mantel-Haenszel
CRF	case report form
CSR	clinical study report
C-SSRS	Columbia-Suicide Severity Rating Scale
EOS	end of study
EOT	end of treatment
FAS	full analysis set
HDL	high density lipoprotein
HOMA-IR	Homeostatic Model Assessment of Insulin Resistance
LDL	low density lipoprotein
LS	least squares
MedDRA	Medical Dictionary for Regulatory Activities
MMRM	mixed effect model repeated measurement analysis
PD	pharmacodynamics
PHQ-9	Patient Health Questionnaire
PK	pharmacokinetic
PP	per-protocol analysis set
PT	preferred term
QD	once daily
SAE	serious adverse event
SAP	statistical analysis plan
SD	standard deviation

Abbreviation	Term
SOC	System Organ Class
TEAE	treatment-emergent adverse event
TLG	tables, listings, and graphs
WHO DD	World Health Organization Drug Dictionary

3 INTRODUCTION

The purpose of this statistical analysis plan (SAP) is to describe the procedures and the statistical methods that will be used to analyze and report results for Eisai Protocol APD356-A001-403.

Since this study has been terminated early and when only about 20% of subjects have completed week 52 visit, many of the planned efficacy outputs will not show enough data as initially planned for this study. Most planned efficacy tables will not be produced. For details on changes in planned analysis, please see section 7 “Changes in Planned Analysis”.

This document is prepared based on the final study protocol (protocol V10.0 12Feb2018). Reader is referred to the final study protocol, the case report form (CRF), general CRF completion guidelines for details of study design, conduct and data collection.

3.1 Study Objectives

3.1.1 Primary Objective

- To demonstrate weight loss efficacy by change in body mass index (BMI) during 52 weeks of treatment with Belviq XR 20 mg administered QD as compared to placebo

3.1.2 Secondary Objectives

Key Secondary Objective

To demonstrate weight loss efficacy by achieving a greater proportion (%) of subjects with a at least a 5% reduction in BMI during 52 weeks of treatment with Belviq XR 20 mg administered QD as compared to placebo

3.1.3 Other Secondary Objectives

- To demonstrate weight loss efficacy by achieving a greater proportion (%) of subjects with at least a 5% reduction in BMI after an initial 12 weeks of treatment with Belviq XR 20 mg administered QD compared to placebo
- To demonstrate that achieving at least a 5% reduction in BMI after an initial 12 weeks of treatment with Belviq XR 20 mg administered QD is predictive of sustained change in BMI during 52 weeks of treatment with Belviq XR 20 mg administered QD
- To demonstrate weight loss efficacy by percentage change from baseline in BMI during 52 weeks of treatment with Belviq XR 20 mg administered QD compared to placebo
- To demonstrate the efficacy of treatment with Belviq XR 20 mg QD by assessing:

- Other weight loss effects (e.g., proportion [%] of subjects achieving at least a 10% BMI reduction, change in waist circumference) at the end of 52 weeks of treatment
 - Effects on fasting glucose, hemoglobin A1c (HbA1c), insulin levels, and Homeostatic Model Assessment of Insulin Resistance (HOMA-IR; $\text{glucose [mg/dL]} \times \text{insulin [mU/L]}/405$) in subjects with Type 2 diabetes at baseline during 52 weeks of treatment
 - Effects on fasting glucose, HbA1c, insulin levels, and HOMA-IR; $\text{glucose [mg/dL]} \times \text{insulin [mU/L]}/405$ in subjects without Type 2 Diabetes at Baseline during 52 weeks of treatment
 - Effects on body fat and lean mass composition by Dual-energy X-ray Absorptiometry (DEXA) in a subset of randomized subjects (selected prior to randomization) at selected sites during 52 weeks of
 - Changes in cardiovascular risk factors associated with obesity (e.g., hypertension, dyslipidemia) including fasting lipid changes (total cholesterol, triglycerides, high density lipoprotein [HDL], low density lipoprotein [LDL]), systolic and diastolic blood pressure, and heart rate) during 52 weeks of
- To assess the safety of Belviq XR, including the effects on cognition by Leiter-3 International Performance Scale (Leiter-3), depression with the Patient Health Questionnaire (PHQ-9), signal of suicidal ideation or behavior with the Columbia-Suicide Severity Rating Scale (C-SSRS), growth measured by CDC growth chart, sexual maturation (pubescence) measured by Tanner Staging scores, and other growth and development parameters by measuring sex hormones, thyroid function, adrenal function, bone age, and biochemical markers of bone health, bone mineral density and content, total body fat mass and total body lean mass by DEXA in a subset of randomized subjects (selected prior to randomization) at selected sites, valvular function, pulmonary arterial pressure.
 - To assess the pharmacokinetic (PK) of lorcaserin using population PK modeling
 - To assess relationships between plasma exposure to lorcaserin and pharmacodynamics (PD) parameters including but not limited to reduction from baseline in BMI and probability of achieving at least a 5% and at least a 10% reduction in BMI from baseline at Week 52 using population PK/ PD modeling

3.2 Overall Study Design

This is a multicenter, randomized, double-blind, placebo-controlled, parallel-group study in obese adolescents ages 12 to 17 years. Approximately 260 subjects will be randomized in a 1:1 ratio to Belviq XR 20 mg QD (130 subjects) and placebo (130 subjects). Subjects will be stratified by sex. Subjects will receive Belviq XR 20 mg or matched placebo QD in a 1:1 ratio for up to 52 weeks. A recruitment plan will be developed to ensure at least 20% of younger subjects (12 to 13 years of age) are enrolled in the study.

Throughout the duration of the study, subjects will be encouraged to adhere to a lifestyle modification program that includes a standardized, age-appropriate diet and exercise counseling (see [Appendix 2](#)).

The study will consist of 2 phases: Prerandomization and Randomization. The Prerandomization Phase will last up to 30 days and consists of 1 visit during which subjects will be screened for eligibility. The Randomization Phase consists of a Treatment Period and a Follow-Up Period. The Treatment Period will last for a maximum of 52 weeks, with visits at Weeks 1, 5, 8, 12, 20, 28, 36, 44, and 52; the Follow-Up Period will extend from the End of Treatment (EOT) visit to the End of Study (EOS) visit.

Subjects who screen fail can be rescreened only once. All subjects will continue in the study until the 52-week evaluation is completed. Subjects who discontinue treatment prematurely will be followed up until study completion. All attempts will be made to capture height and weight in all subjects whether or not they are still on study drug at the end of the study.

Details of the study procedures and schedule of assessments can be found in Table 2 of the protocol.

4 DETERMINATION OF SAMPLE SIZE

The proposed sample size is based on the comparison of the primary efficacy endpoint, change from baseline in BMI at Week 52 between the Belviq XR 20-mg treatment group and placebo group.

Assuming a SD of 2.2 kg/m² and a 40% dropout rate, a sample size of 260 subjects in a 1:1 ratio (n=130 in the Belviq XR 20-mg treatment group; n=130 in the placebo group) will have at least 80% power to detect a treatment difference of 1 kg/m² in BMI, using a 2-sided t-test with $\alpha=0.05$.

Assuming the proportion of subjects achieving at least a 5% BMI reduction at Week 52 is 20% for the placebo group and a 40% dropout rate, this sample of 260 subjects (130 subjects for Belviq XR 20 mg and 130 subjects for placebo) will also have greater than 78% power to detect an absolute difference of 20% between the Belviq XR 20-mg group and placebo group, using a 2-sided Chi-Square test with $\alpha=0.05$.

The assumption used in the sample size calculation is based on the 2 pivotal lorcaserin studies, APD356-009 and APD356-011 in obese and overweight non-diabetic adult subjects. (Revised per Amendment 02)

5 STATISTICAL METHODS

Descriptive statistics will be reported for continuous variables using mean, standard deviation (SD), median, minimum and maximum. Categorical variables will be summarized using frequency count as number (percentage) of subjects.

5.1 Study Endpoints

5.1.1 Primary Endpoint

- Change in BMI from Baseline to Week 52

5.1.2 Secondary Endpoints

KEY SECONDARY ENDPOINT

- Proportion (%) of subjects achieving at least a 5% BMI reduction at Week 52

OTHER SECONDARY ENDPOINTS

- Proportion (%) of subjects achieving at least a 5% BMI reduction at Week 12
- Proportion (%) of subjects achieving at least a 10% BMI reduction at Week 52
- Percentage change in BMI from Baseline to Week 52
- Association between change and percentage change in BMI from Baseline to Week 52 with the outcome of achieving at least a 5% BMI reduction at Week 12 (revised per Amendment 02)
- Association between the proportion (%) of subjects achieving at least a 5% or 10% BMI reduction at Week 52 with the outcome of achieving at least a 5% BMI reduction at Week 12 (revised per Amendment 02)
- Change in waist circumference from Baseline to Week 52
- Change in total body composition (total fat and lean mass) in a subset of randomized subjects at end of 52 weeks of treatment (revised per Amendment 03)
- Change in HbA1c from Baseline to Week 52 for subjects with Type 2 diabetes at baseline (revised per Amendment 03)
- Change in fasting glucose, fasting insulin, and HOMA-IR from Baseline to Week 52 for subjects with Type 2 diabetes at baseline (revised per Amendment 03)
- Change in fasting glucose, fasting insulin, and HOMA-IR from Baseline to Week 52 for the subjects without Type 2 diabetes at baseline (revised per Amendment 03)

- Change in BP (systolic and diastolic) and heart rate from Baseline to Week 52
- Change in fasting lipid profile (total cholesterol, LDL cholesterol, HDL cholesterol, triglycerides) from Baseline to Week 52
- Proportion (%) of subjects with prehypertension or primary hypertension at Week 52
- Proportion (%) of subjects with dyslipidemia at Week 52
- Subject compliance rate at each visit by pill count during 52 weeks of treatment (per Amendment 03)

5.2 Study Subjects

5.2.1 Definitions of Analysis Sets

The Safety Analysis Set is the group of subjects who received at least 1 dose of study drug and had at least 1 post dose safety assessment.

The Full Analysis Set (FAS) is the group of all randomized subjects who received at least 1 dose of study drug.

PK Analysis Set: the PK analysis set is the group of subjects who have at least 1 quantifiable plasma concentration of lorcaserin with adequately documented dosing history.

The number (percentage) of subjects in each analysis set will be summarized by treatment groups using descriptive statistics.

5.2.2 Subject Disposition

The number of subjects screened and the number (percentage) of subjects who failed screening and the reasons for screen failure will be summarized, based on data reported on the CRF.

For study completion, the number (percentage) of treated subjects who completed study treatment and who discontinued from study treatment will be summarized according to the primary reason for discontinuation and also according to secondary reason(s) for discontinuation, based on data reported on the CRF. The number (percentage) will be presented by treatment. The reasons for discontinuation from study treatment will be documented in the CRF and source documentation.

5.2.3 Protocol Deviations

Major protocol deviations will be identified, reviewed and documented by the clinical team prior to database lock/treatment unbinding. All protocol deviations will be categorized according to standard classifications including the following:

- Violations of inclusion/exclusion criteria

- Noncompliance with protocol procedures/assessments
- Noncompliance of drug dosage
- Use of prohibited treatments

All significant protocol deviations will only be presented in the listings.

5.2.4 Demographic and Other Baseline Characteristics

Demographic and other baseline characteristics for the FAS and Safety Analysis set will be summarized for each treatment group and overall using descriptive statistics or frequency count. Continuous variables include age, weight, height, body mass index (BMI) and waist circumference; categorical variables include age group, sex, ethnicity, and race.

MEDICAL HISTORY

All medical histories as documented by the Investigator will be coded using the Medical Dictionary for Regulatory Activities (MedDRA).

The number (percentage) of subjects reporting a history of any medical condition, as recorded on CRF, will be summarized by System Organ Class (SOC), preferred term for each treatment group and overall based on FAS.

5.2.5 Prior and Concomitant Therapy

All investigator terms for medications recorded in the CRF will be coded to an 11-digit character code using the World Health Organization Drug Dictionary (WHO DD).

Prior medications are defined as medications that stop prior to the first dose of study drug. Concomitant medications are defined as medications that (1) start before the first dose of study drug and are continuing at the time of the first dose of study drug, or (2) start on or after the date of the first dose of study drug, up to 30 days after the last dose of study drug.

The number (percentage) of subjects who took prior and concomitant medications will be summarized for the Safety Analysis Set by treatment group, Anatomical Therapeutic Chemical class, and WHO DD preferred term (PT). If a subject takes the same medications for the same class level or drug name, the subject will be counted only once for that class level or drug name.

5.2.6 Treatment Compliance

Treatment compliance is defined as follows: Total number of tablets dispensed – total number of tablets lost or returned divided by total number of tablets subject should have taken.

Treatment compliance will be summarized using descriptive statistics by treatment group based on FAS and Safety Analysis Set. Treatment compliance will also be summarized by treatment group using the categories <80%, ≥80% to ≤100%, >100% to ≤120%, and >120%.

5.3 Data Analysis General Considerations

The FAS will be used for all efficacy analyses, and since study has been terminated early, there will be no additional supportive or sensitivity analysis.

5.3.1 Pooling of Centers

No pooling of centers will be done since there will be no ANCOVA analysis.

5.3.2 Adjustments for Covariates

There will be no analysis of covariance and only basic summary of descriptive statistics will be performed for the BMI.

5.3.3 Multiple Comparisons/Multiplicity

No adjustment for multiplicity is planned for other secondary endpoints, subgroup, and sensitivity analyses.

5.3.4 Examination of Subgroups

Subgroup analyses will be performed on the primary efficacy endpoint using age group (<12, 12 - <13, 13 - <14, 14 - <15, 15 - <16, 16 - <17, 17 - <18 and > 18 yrs.), sex (male and female), race (white, black, Asian, and other). Additional subgroup analysis may also be explored, if deemed appropriate.

5.3.5 Handling of Missing Data, Dropouts, and Outliers

Due to the early termination of the study, no imputation analysis will be performed.

5.3.6 Other Considerations

Due to the early termination of the study, only simple summary of descriptive statistics will be provided for efficacy endpoint.

Individual subject data in the database will be presented in data listings.

The following rules/definitions will be applied in the final outputs:

- Homeostatic Model Assessment of Insulin Resistance (HOMA-IR Fasting insulin (mIU/L) x Fasting glucose (mmol/L) / 22.5)
- Dyslipidemia: Please use the following link: (https://www.nhlbi.nih.gov/files/docs/peds_guidelines_sum.pdf) and consider subject “with Dyslipidemia” if TC \geq 170 or LDL-C \geq 110 or Non- HDL-C \geq 120 or TG \geq 90 or HDL-C \leq 40. Values given are in mg/dL. **To convert to SI units, divide the results for total cholesterol (TC), low-density lipoprotein cholesterol (LDL-C), high-density**

lipoprotein cholesterol (HDL-C), and non-HDL-C by 38.6; for triglycerides (TG), divide by 88.6.

- Prehypertension or Hypertension:

BP is classified as SBP and DBP percentiles for age/sex/height.

Prehypertension: If SBP or DBP $\geq 90^{\text{th}}$ percentile or $< 95^{\text{th}}$ percentile or BP $> 120/80$ mmHG to $< 95^{\text{th}}$ percentile

Hypertension: If SBP or DBP $\geq 95^{\text{th}}$ percentile or BP $\geq 95^{\text{th}}$ percentile

- Subjects who are type 2 diabetes (T2DM) at Baseline are defined as follows:

Positive diagnosis of diabetes (Preferred Term: *Type 2 diabetes mellitus*) based on Medical History Form or AE with the start date prior to the first dose of the study drug.

The formula for BMI is weight in kilograms divided by height in meters squared.

Continuous variables will be summarized using the following descriptive summary statistics: the number of subjects (n), mean, standard deviation (SD), minimum value (min), and maximum value (max). Minimum and maximum values will be reported with the same precision as the units of measure. The mean and median will be reported to 1 greater decimal place, and the SD will be reported to 2 additional decimal places.

Categorical variables will be summarized using counts and percentages. Percentages will be presented to 1 decimal place.

Baseline Value: The baseline value will be defined as the most recent non-missing measurement (scheduled or unscheduled) collected prior to the initial administration of study drug. Unscheduled visit measurements will be included for derivation of baseline.

Change (Absolute Change) from baseline: will be calculated as Post baseline value - Baseline value.

Percent change from baseline: will be calculated and expressed in percentages as $100 \times (\text{Post baseline value} - \text{Baseline value}) / \text{Baseline value}$.

Unscheduled Visits: Unscheduled visit measurements will be included in listings, for derivation of visit windows and computation of baseline/last on-treatment visit.

Outliers: No formal statistical analyses will be performed to detect and/or remedy the presence of statistical outliers.

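### SAP 5.3.6 joins the two percentile bounds for prehypertension with *or*, so every blood pressure reading meets the rule and the Week 52 endpoint, applied as written, carries no information

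*SAP*

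**What the plan says.** Section 5.1.2 lists among the other secondary endpoints: "Proportion (%) of subjects with prehypertension or primary hypertension at Week 52". The definitions are in section 5.3.6, introduced by "The following rules/definitions will be applied in the final outputs". The scale is stated first: "BP is classified as SBP and DBP percentiles for age/sex/height". Prehypertension is then defined by "Prehypertension: If SBP or DBP $\geq 90^{\text{th}}$ percentile or $< 95^{\text{th}}$ percentile", and the same sentence goes on "or BP $> 120/80$ mmHG to $< 95^{\text{th}}$ percentile". The next line reads "Hypertension: If SBP or DBP $\geq 95^{\text{th}}$ percentile or BP $\geq 95^{\text{th}}$ percentile".

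Nothing else in the SAP corrects the connective or says which category takes precedence. Section 7 lists the changes made because of early termination. It removes the type 2 diabetes endpoints by name but does not mention this one.

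**The concern.** A band between two limits needs both limits to hold. Joined by *or*, a lower limit of 90 and an upper limit of 95 exclude nobody. A subject with ordinary blood pressure is then a case, and so is a subject in the hypertension range. The endpoint counts subjects in either category, so it cannot distinguish the arms or show change over time.

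All efficacy output is now descriptive, so for this endpoint the reported percentage is the whole result. If a programmer instead reads *and*, the table will be sensible but will not follow the signed plan, and nothing will document the departure.

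**Working it through.** The SAP states no prevalence or power for this endpoint, so there is no figure to reproduce. The check is one of logic, using the rules in section 5.3.6.

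**1. One pressure, by percentile zone p.**

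| Zone | p ≥ 90 | p < 95 | Joined by *or* (as written) | Joined by *and* |
|---|---|---|---|---|
| p < 90 | no | yes | case | not a case |
| 90 ≤ p < 95 | yes | yes | case | case |
| p ≥ 95 | yes | no | case | not a case |

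The union of {p ≥ 90} and {p < 95} is the whole scale. The 120/80 clause is joined by a further *or*, so it can add cases but cannot remove any.

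**2. Both pressures.** The sentence can be parsed in more than one way, so it was run over a grid of systolic and diastolic percentiles from 0 to 99.5 in steps of 0.5, which is 200 × 200 = 40,000 pairs:
- either pressure meets the percentile clauses: 100% of pairs are cases;
- both pressures must meet them: 100%;
- either pressure ≥ 90th, or both < 95th: 100%. If neither pressure reaches the 90th, both are below the 95th.

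No parse rescues the rule. A subject at the 50th percentile on both pressures is a case under each.

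**3. Effect on the endpoint.** Let f be the fraction of an arm's analysis set with a Week 52 reading. Under the literal rule:
- denominator = subjects with a Week 52 reading: proportion = f / f = 100% in each arm, difference 0;
- denominator = all of the full analysis set, without imputation: proportion = f in each arm, difference = f(active) − f(placebo).

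Section 3 says only about 20% of subjects had completed the Week 52 visit. The second version would therefore measure who reached Week 52, not blood pressure.

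**4. After changing *or* to *and*.** The SAP gives no blood pressure distribution, so this step rests on an assumption: percentiles uniform, as in a reference population, with the 120/80 clause set aside.
- The two pressures fully correlated: prehypertension 5% + hypertension 5% = 10%.
- The two pressures independent: either category = 1 − 0.90² = 19%, of which hypertension = 1 − 0.95² = 9.75% and prehypertension only = 19% − 9.75% = 9.25%.

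An obese adolescent sample may differ. The 10% to 19% range shows only that the endpoint can now vary.

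**5. Overlap.** Changing the connective does not by itself make the categories exclusive. A subject with one pressure in the band and the other at or above the 95th still meets both rules. In the independent case that is 2 × 0.05 × 0.05 = 0.5% of subjects. The combined proportion counts such a subject once, so it stays at 19%. Only separately reported categories are affected.

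**The case against.** The strongest reply is that the intended meaning is plain. Two bounds are given, the next clause runs up to the 95th percentile, and hypertension starts there. A programmer would probably read *and*. Section 9 leaves derivation rules to separate specifications, which are not at hand and may have the rule right. This stands as an argument about likelihood. It does not correct the SAP, and section 5.3.6 says its definitions govern the final outputs.

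The second reply is that little depends on this endpoint. It is one of many other secondary endpoints, with no test attached. Section 3 warns "Most planned efficacy tables will not be produced", and the analyses listed in section 5.4.3 all concern BMI. Section 5.6.4 summarises systolic and diastolic pressure by visit and arm, and section 5.3.6 provides individual listings, so a misclassification would be visible and recoverable. This also stands, and it limits the severity. It does not show that the endpoint was dropped: section 3 refers to section 7 for the changes, and section 7 keeps descriptive summaries without naming this endpoint.

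A reader might infer that the reported result will be 100% in both arms at every visit, with zero difference whatever the data. The documents do not support that. The endpoint is defined at Week 52 only, the figure requires literal programming, and the SAP does not state the denominator. A reader might also think that the overlap of the two categories distorts the endpoint. It does not change the combined proportion.

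**Conclusion.** The rule is wrong as written: every blood pressure reading satisfies it. The combined Week 52 proportion would be 100% in both arms, and uninformative, on two conditions: the text is programmed literally, and the denominator is subjects with a Week 52 reading. With the full analysis set as denominator it would equal the fraction with a reading, which is no more useful.

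Severity is minor to moderate. It would be tempting to call this a defect that must be cured before any analysis can proceed. That goes too far for a descriptive other secondary endpoint whose table may not be produced and whose underlying values are summarised elsewhere. No primary or key secondary result is touched.

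Changing *or* to *and* follows from the bounds in the text. How the 120/80 clause combines the two pressures does not follow from the text, and any reading of it would be an assumption.

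**What to change.** In section 5.3.6:

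1. Replace *or* with *and* between the two percentile bounds, so that the band is at or above the 90th and below the 95th percentile.
2. Classify hypertension first, and state that a subject with either pressure at or above the 95th percentile is counted there only. This keeps separately reported categories from overlapping and leaves the combined proportion unchanged.
3. Have the sponsor state whether one or both pressures must exceed 120/80 in the last clause.
4. State that the denominator is subjects with a Week 52 reading, if that is what is intended.

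If the table will not be produced, delete the definition and add the endpoint to the list of dropped analyses in section 7.

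The cost is a few lines of SAP text and a matching check of the derivation program. Only item 3 needs a decision that the text does not already imply. No new data are needed.
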